**Table 1 Schedule of Activities – Main Table**

Activity	Screening / Baseline a		Dose 1			Dose 1 Outpatient Visits				Dose 2		Outpatient Phone Call	Outpatient visit	Dose 3		Outpatient Phone Call	Outpatient visit
	D-36 to D-2	D-1	Day 1	Day 2	Day 4	Day 6	Day 8	Day 10	Day 15	Day 16	Day 19	Day 22	Day 29	Day 30	Day 33	Day 36	
Overall Study Day																	
Dose/Day		Dose 1/Day -1	Dose 1/Day 1	Dose 1/Day 2	Dose 1/Day 4	Dose 1/Day 6	Dose 1/Day 8	Dose 1/Day 10	Dose 2/Day 1	Dose 2/Day 2	Dose 2/Day 5	Dose 2/Day 8	Dose 3/Day 1	Dose 3/Day 2	Dose 3/Day 5	Dose 3/Day 8	
Time Relative (h)	***	***	0	24	72	120	168	216	336	360	432	504	672	696	768	840	
Visit Window						(+/-1)	(+/-1)				(+/-1)	(+/-1)	(+/-1)	(+/-1)	(+/-1)	(+/-1)	
Assessments																	
Informed Consent b	X																
Demography	X																
Medical History	X																
Randomization c	X																
Physical Examination d	X	X	X	X						X				X			
Vital Signs e	X	X	2	X						X	X			X	X		
Eligibility	X	X															
Tuberculosis Screening Test f	X																
Clinical Genotyping g		X															
ECG-12 lead h	X		2	X						X				X			
Hematology i	X	X		X			X		X				X	X		X	
Blood Chemistry i	X	X		X			X		X				X	X		X	
Urinalysis i	X	X		X			X		X				X	X		X	
Serology and viral PCR j	X																
Pregnancy Testing k	X	X								X				X			
Coagulation	X																
Alcohol breath or blood test	X	X															
Drugs of abuse l	X	X															
Colonoscopy or flexible sigmoidoscopy m	X													X			
Colon Biopsy	X													X			
Stool Clostridium difficile n	X																
Stool Ova and Parasites	X																
In-house period		X	X	X						X	X			X	X		
Drug/Placebo Administration			X							X				X			
Standard meal o		X	X	X						X	X			X	X		
PK sampling p			3	X	X	X	X	X	X	2			X	X		X	
Blood flow cytometry		X	X	X			X	X	X	X			X	X		X	
Blood epigenetic testing			X			X	X	X	X	X							
Soluble PD biomarkers q			X	X	X	X	X	X		X				X			
Soluble disease biomarkers n			X	X						X				X			
sCD25 w		X	X			X	X	X		X				X			
Fecal Calprotectin v			X							X							
Abdominal skinfold thickness			X														
Anti-drug antibodies			X						X	X			X	X			
Local pain/Skin reactivity assessments x			X						X				X				

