**Table 1 Schedule of Activities – Main Table (cont.)**

- o) Standard breakfast, lunch, dinner and snack to be provided at the times deemed convenient by the site.
- p) For exploratory PD cytokines and other soluble markers.
- q) LRG and ANCA screen. Based on outcome of ANCA screen, p-ANCA, c-ANCA, and atypical p-ANCA may be tested. LRG is optional.
- r) And at additional regular intervals at the Investigator's discretion if an adverse event associated with local tolerability and pain is observed.
- s) Partial Mayo Score.
- t) Site personnel will contact the participant. If deemed required by the Investigator, participants can be asked to come to the site for an unscheduled visit.
- u) IgE, tryptase and exploratory safety biomarkers may be tested in case of participants experiencing signs and symptoms associated with injection-related reactions (IRRs). This includes hypersensitivity reactions.
- v) The Day 50 stool sample for measuring fecal calprotectin can be taken +/- 2 days. The other stool samples should be collected +/- 1 day.
- w) Participants positive for anti-drug antibodies (ADA) will be requested to return and have additional ADA and sCD25 samples to monitor off-treatment ADA persistence.
- x) *Safety laboratory assessments on Day 50 are only for participants enrolled in dose level 3 (15 mg, Q2W).*
- y) *PK samples collected within 24 hours post-dose, can be taken with a deviation of  $\pm$  15 minutes for samples taken up to 6 hours after dosing with RO7049665/ placebo, and for samples thereafter with a deviation of  $\pm$  30 minutes.*

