**Table 2 Schedule of Activities - Detailed Table**

Visit	Day	Scheduled Time (h)	Vital Signs b	Physical Examination c	ECG-12 lead d	PK Sample e	ADA	Blood Flow Cytometry	Blood Epigenetic Testing	sCD25	Local Pain and Skin Reactivity
Dose 1 in-house period a	Day -1		x	x			x	x			
	Predose		x		x	x		x	x	x	
	0										
	2		x								
	6			x		x					
	12				x	x					x
Dose 1 outpatient visits	Day 24		x	x	x	x		x		x	
	Day 4					x					
	Day 6					x		x	x	x	
	Day 8					x	x	x	x	x	
Dose 2 in-house period	Day 10					x		x	x		
	Predose		x	x	x	x	x	x	x	x	
	0										
	12				x						x
Dose 2 outpatient visit	Day 15		x								
Dose 3 in-house period	Day 16										
	Day 22					x	x	x			
	Predose		x	x	x	x	x	x		x	
	0										
Dose 3 outpatient visit	Day 29		x								
	Day 12										x
	Day 30		x								
	Day 36					x		x			
Dose 4 in-house period	Predose		x	x	x	x	x	x	x	x	
	0										
	Day 43		x								
	2										
	6				x						
Dose 4 outpatient visits	12				x	x					x
	Day 44	24	x		x	x				x	
	Day 46					x					
	Day 48					x		x	x	x	
	Day 50					x		x	x	x	
	Day 52					x		x	x	x	
Follow Up visit	Day 57					x	x	x	x		
	Day 71					x	x	x	x	x	
Unscheduled visit	Anytime		x	x	x	x	x	x	x	x	x
Hypersensitivity/ IRR (≥ Grade 2)	Anytime		x	x		x	x				x
Early Termination Visit	Anytime		x		x	x	x				x

RO7049665—F. Hoffmann-La Roche Ltd

26/Protocol WP40161, Version 5

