### Study WP40161

*In this ongoing study WP40161, to date, multiple doses (i.e., up to 4) of 3.5 mg and 7.5 mg have been well tolerated, and they induced dose-dependent  $T_{reg}$  cell expansions up to 5-fold (mean at the highest dose of 7.5 mg) versus baseline.*

*The most frequently reported AEs were injection site reactions (ISRs) and eosinophilia. The majority of AEs reported were mild or moderate (Grade 1 or 2) in intensity except for a low number of events of severe (Grade 3) intensity, including anemia, eosinophilia and hyperkalemia. No events of CLS were reported. Hypersensitivity reactions (Grade 2)*

*with some, or all, symptoms of erythema, edema of the forearm, scapula and right arm, have been reported, as well as injection-related reactions (IRR) with some, or all, symptoms of myalgia, fatigue, chills and redness of face and neck. All events either have resolved without sequelae or are ongoing. There have been no deaths reported to date.*

*Immunogenicity was assessed, and positive results for ADA were observed in approximately 50% of participants. There have been no results to date indicating ADAs with neutralizing potential against endogenous IL-2. The ADAs were not associated with changes in PK parameters, and did not impact exposure or PD.*

*No significant abnormalities on vital signs or ECG intervals have been reported to date and, besides the changes on eosinophils, no significant laboratory safety results have been noted in participants with UC receiving up to 4 doses of 3.5 mg and 7.5 mg Q2W of RO7049665.*

Detailed descriptions of the chemistry, pharmacology, pharmacokinetics, efficacy and safety of RO7049665 are provided in the [RO7049665 Investigator's Brochure](#).

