Concomitant therapy with immunomodulators such as azathioprine/6-mercaptopurine (6-MP)/methotrexate may decrease the risk of ADA and neutralizing IL-2 antibody formation. Patients who are already on one of these therapies will continue; patients who are not already on these therapies will not be proactively started on them. The mechanism of action of RO7049665 is to induce tolerance via increases in  $T_{reg}$  activity. This tolerance induction can potentially mitigate the risk of ADA and neutralizing IL-2 antibody formation.

- **Increased Regulatory T Cells Causing Immunosuppression**

There is a theoretical risk of immunosuppression from increased  $T_{reg}$  cell count and an increased proportion of  $T_{regs}$  compared with total T cells. Infections, especially opportunistic infections, and malignancies are theoretical risks. Signs and symptoms of immunosuppression will be monitored and treated according to standard of care. A stopping criterion specific for  $T_{regs}$  increases has also been included.

- Injection Site Reactions

Localized injection site reactions (including erythema, pruritus and swelling) of mild intensity and resolving without treatment were observed following dosing with RO7049665 in the WP39826 study. There was a higher incidence at higher doses and injection site erythema was the most frequently observed event. The erythema was first observed at 2 to 6 days after dosing and had a duration varying from 3 to 54 days until complete resolution. Assessments of local skin reactivity and pain following injection will be performed in this study to further characterize injection site reactions. Administration of serial doses in the same *participant* should be done in different quadrants of the abdomen.

- Non-clinical Finding of Heart Rate Increase

Heart rate increases were observed in the 13-week good laboratory practice (GLP) study in cynomolgus monkeys. The heart rate increases showed complete reversibility in recovery. The effects seen on heart rate were likely linked to the acute phase response and/or elevated cytokine levels, both of which were more pronounced after Week 1 and thus are considered secondary to the pharmacologic action of the study drug. These effects were completely reversible. No trend towards increased heart rate was observed in the WP39826 clinical study after single dosing. Vital signs and ECGs will be monitored in this study. Further details are provided in the [RO7049665 Investigator's Brochure](#).

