### 4. STUDY DESIGN

#### 4.1 OVERALL DESIGN

Study WP40161 is a multicenter, randomized, adaptive, Investigator and participant blind, placebo-controlled study to investigate the safety, tolerability, PK, PD, and

preliminary efficacy of multiple ascending doses (MAD) of RO7049665 on top of standard of care (SOC) in participants with endoscopic evidence of moderate to severely active UC. The participants, investigators, and site personnel will be blinded to treatment assignments.

Since this is the first clinical study in which RO7049665 will be tested in participants diagnosed with UC and the first study in which multiple doses of RO7049665 will be administered, a dose escalation design will be used.

All participants in the study will have evidence of active disease on endoscopy at screening (MCS  $\geq 5$ , Endoscopy subscore of the Mayo Clinic Score [MCS-ES]  $\geq 2$ , stool frequency subscore  $\geq 1$ , and rectal bleeding subscore  $\geq 1$ ). Participants will be eligible for the study if they are currently receiving non-biologic SOC therapy for UC and have not been treated with any biologic therapy within 3 months (or 5 half-lives, whichever is longer) before the start of screening.

Participants will be randomized in a 4:1 ratio to receive multiple SC injections of RO7049665 or placebo, respectively (approximately 8 on active and 2 on placebo per cohort). Participants will receive their first doses in a staggered manner, with a five-day interval between the *first dose of the first, second, and third participants*. *The fourth participant can receive the first dose 14 days after the first dose of the third participant, at the earliest. There will be a 48-hour interval between the first dose of subsequent participants in each dose level.* Based on emerging data, dose levels may be expanded.

The dosing interval will be every 2 weeks (Q2W), for 4 doses. The first dose level will be 3.5 mg, the second dose level will be 7.5 mg *and participants enrolled in the cohorts of dose level 3 will receive 15 mg of RO7049665 (or placebo).* The doses are based on safety, tolerability, PK and PD data derived from study WP39826 (see Section 4.3) and *review of data from completed cohorts in this study.* Each dose level will have cohorts of approximately 10 participants, randomized in the ratio of 4:1 RO7049665 to placebo. Based on the emerging data there may be more than one cohort enrolled per dose level.

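### No routine injection-site score falls in or shortly after the 2 to 6 day erythema onset window, so erythema severity and size after each dose are not measured at a common time

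*Combined protocol and SAP*

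**What the plan says.** Section 2.3 (Injection Site Reactions) describes the single-dose healthy-volunteer study WP39826. There, "injection site erythema was the most frequently observed event", and its timing is given: "The erythema was first observed at 2 to 6 days after dosing and had a duration varying from 3 to 54 days". The same bullet states the purpose of the scoring here: "Assessments of local skin reactivity and pain following injection will be performed in this study to further characterize injection site reactions".

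Section 8.2.7 leaves the timing to the Schedule of Activities. In Table 2 the column "Local Pain and Skin Reactivity" is marked once per dose, in the 12-hour row, for all four doses. In Table 1 the row "Local pain/Skin reactivity assessments" is marked on the dosing days (1, 15, 29, 43), then at Day 99 and at the unscheduled, hypersensitivity/IRR and early termination visits. Footnote r provides for more: "And at additional regular intervals at the Investigator's discretion if an adverse event associated with local tolerability and pain is observed".

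Appendix 6 defines a 100-mm pain VAS, a 0–3 reactivity scale and a 0–4 size scale. Section 4.1 sets the dosing: "The dosing interval will be every 2 weeks (Q2W), for 4 doses". On this study so far, Section 2.2.2.1 says: "The most frequently reported AEs were injection site reactions (ISRs) and eosinophilia".

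**The concern.** The only scheduled post-dose score comes before the reaction it is meant to describe, on the protocol's own account of timing. Participants attend on Days 4, 6, 8, 10, 22, 36, 46, 48, 50 and 52, yet none of those visits carries a routine skin score.

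Safety and tolerability is the primary objective. Injection-site reactions are among the most frequent events in this study, and in WP39826 they affected more participants as the dose rose (Section 2.2.2.1). Version 5 doubles the top dose to 15 mg. At the 5 mg/mL strength in Table 5, undiluted, that is 15/5 = 3.0 mL against 7.5/5 = 1.5 mL. At stake is whether erythema severity and size can be described at the same time after each dose, on active and on placebo. Otherwise they are known only from scores triggered by a noticed event.

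**Working it through.** **Inputs**
- Erythema onset 2 to 6 days, duration 3 to 54 days (Section 2.3). No distribution is given for either.
- Scheduled score: 12 h = 0.5 day after each dose (Table 2). Dosing days 1, 15, 29, 43.
- Visits 7 days after each dose, from the relative hours in Table 1: Day 8 = 168 h; Day 22 = 504 − 336 = 168 h; Day 36 = 840 − 672 = 168 h; Day 50 = 1176 − 1008 = 168 h.
- The columns of Tables 1 and 2 are partly displaced in the text copy. The reading rests mainly on the 12-hour rows of Table 2. Day 99 is read by column position in Table 1.

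**1. The plan's own figure.** The plan gives no figure for these scores. Its only design probabilities (Section 9.2) reproduce: 1 − 0.8^8 = 0.832 and 1 − 0.8^4 = 0.590, stated as 83% and 59%. They are not inputs here.

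**2. The 12-hour score against onset.** It precedes the earliest onset by 2 − 0.5 = 1.5 days and the latest by 6 − 0.5 = 5.5 days. The onset windows (dose day + 2 to dose day + 6) are study Days 3–7, 17–21, 31–35 and 45–49. Scheduled scores inside them: 0 of 4.

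**3. The next scheduled score.** At doses 2 to 4 the 12-hour score falls 14 + 0.5 = 14.5 days after the previous dose. Erythema from that dose is still present only if it lasted more than 14.5 − 6 = 8.5 days (latest onset) to 14.5 − 2 = 12.5 days (earliest onset). Assuming onset uniform on 2–6 days, the simulated share still present depends on the duration shape assumed on 3–54 days:

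| Assumed duration | Median (days) | Present at 14.5 d | Present at 7 d |
|---|---|---|---|
| Uniform | 28.5 | 85% | 99.0% |
| Log-uniform | 12.7 | 57% | 95.2% |
| Short-skewed, 3 + 51 × Beta(1,6) | 8.6 | 39% | 94.5% |

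**4. Day 99.** This is 99 − 43 = 56 days after dose 4. Erythema must have lasted more than 56 − 6 = 50 to 56 − 2 = 54 days; the simulated share is about 0% to 4%.

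**5. A score at day 7.** All onsets have occurred by then. A lesion is missed only if onset + duration ≤ 7, which requires onset by day 4 and duration of at most 5 days. For uniform duration the missed share is (1/4)(1/51) × ∫₀² u du = 2/204 = 1.0%, matching the table. If every lesion lasted the minimum 3 days, the share seen would be P(onset > 4) = (6 − 4)/(6 − 2) = 50%.

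**6. Optional earlier scores.** With uniform onset, a score at 3 days (Days 4 and 46) sees (3 − 2)/4 = 25% of eventual erythema, and one at 5 days (Days 6 and 48) sees (5 − 2)/4 = 75%.

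**The case against.** The strongest reply is that late reactions are not lost. Adverse events are sought at every contact (Section 8.3.1) and graded by CTCAE (Appendix 2). Signs and symptoms go on a dedicated Injection Reaction eCRF (Appendix 3). Phone calls on Days 19 and 33 fall 4 days after doses 2 and 3, inside the onset window, and can lead to an unscheduled visit, where the scales are marked. Footnote r calls for repeated scoring once a local event is seen. The primary endpoints do not include the Appendix 6 scores, and Table 7 names no analysis of them. All injection-site events in WP39826 were mild and resolved without treatment.

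This stands as to detection and grading. It does not supply Appendix 6 severity and size scores at a common time in all participants: footnote r is discretionary and follows an observed event. Section 8.3.2 prefers open-ended questioning, which can leave mild erythema unmentioned, and no physical examination is scheduled on Days 4–10 or 46–52.

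A reader might infer that the scheduled scores will mostly read zero. The documents do not support that. The onset figure covers erythema only; Appendix 6 also scores pain, burning, bleeding, itching, bruising and hives, for which no onset is given. Erythema from an earlier dose can persist to the next 12-hour score, and nothing says whether older sites are scored. That makes attribution to a dose ambiguous rather than giving a zero. On the size scale, 0 means that the site could not be assessed. The share of zeros cannot be computed.

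**Conclusion.** The mismatch is real but limited. None of the four scheduled post-dose scores falls in the reported onset window, and the next scheduled look is 14.5 days after the dose or, after dose 4, 56 days. The scoring therefore does not meet its stated purpose for erythema, the most frequent injection-site reaction in WP39826.

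This assumes that single-dose timing in healthy volunteers carries over to repeat dosing in ulcerative colitis; the protocol gives no onset times for this study. The percentages rest on assumed onset and duration distributions and are illustrations only.

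A reader might also infer that 3.5, 7.5 and 15 mg cannot be compared with placebo on local tolerability. That goes too far: incidence and grade can still be compared from adverse event data. What cannot be compared systematically is structured erythema severity and size. No primary endpoint, planned analysis or sample-size statement changes. The change is worth making because it is cheap, not because the trial fails without it.

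**What to change.** In Tables 1 and 2:
- Keep the 12-hour score and add the Appendix 6 scales at the existing visits 7 days after every dose (Days 8, 22, 36 and 50). This gives the same grid for each dose. Days 4, 6, 46 and 48 can be added to describe onset after doses 1 and 4.
- State that the most recent injection site is scored, and that any earlier site still showing a reaction is scored separately and labelled by dose. Section 2.3 already asks for different abdominal quadrants.
- In Section 9.3.2, summarise the day-7 scores by dose level against concurrent placebo, and report footnote r scores separately.

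The cost is schedule wording and a few minutes per visit. Version 5 set the precedent by adding Day 50 laboratory tests for dose level 3 at an existing visit.

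The limits should be stated:
- The grid applies only from the amendment onwards, in practice to dose level 3 and its few placebo participants (about 2 per cohort of 10). It cannot restore a three-dose comparison of the scores.
- A single day-7 score can miss short lesions, and the ±1 day visit windows add to this. Even with the optional visits, a reader should not infer that every reaction would be caught.
- Closer inspection at 15 mg may raise recorded injection-site events relative to earlier cohorts, so cross-cohort adverse event comparisons should note the change.

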### 3. OBJECTIVES AND ENDPOINTS

The objectives and corresponding endpoints are provided in [Table 4](#).

**Table 4 Objectives and Endpoints**

Objectives	Endpoints
Primary	

To evaluate the safety and tolerability of repeat dosing of subcutaneous (SC) injections of RO7049665 in participants with active ulcerative colitis (UC).

	

Incidence of dose-limiting or intolerable treatment-related adverse events (AEs).

Incidence, severity, and causal relationship of treatment-emergent AEs.

Incidence of abnormal laboratory findings.

Incidence of abnormal vital signs and electrocardiogram (ECG) parameters.

Secondary	

To investigate the multiple-dose pharmacokinetics of RO7049665.

	

Pharmacokinetic parameters of RO7049665

To investigate the effects of multiple doses of RO7049665 on changes in endoscopic appearance of the mucosa of the sigmoid colon.

	

Change from baseline in the Endoscopy Subscore of the Mayo Clinic Score (MCS-ES) at Day 29 and Day 57.

Change from baseline in the Ulcerative Colitis Endoscopic Index of Severity (UCEIS) at Day 29 and Day 57.

To investigate the effects of multiple doses of RO7049665 on changes in histologic appearance of mucosa in biopsies from the sigmoid colon.

	

Change from baseline to Day 29 and Day 57 in histology score of sigmoid colon biopsies (Geboes Score [GS], Robarts Histology Index [RHI], or Nancy Histology Index [NHI]).

To investigate the effects of multiple doses of RO7049665 on changes in disease activity.

	

Change from baseline in the Mayo Clinic Score (MCS) at Day 29 and Day 57.

To evaluate the immunogenicity of RO7049665.

	

Incidence of anti-drug antibodies (ADAs).

To investigate the effects of multiple doses of RO7049665 on immune cells in the periphery and in mucosal biopsies of the sigmoid colon.

	

Quantitative changes in WBCs (<math>T_{reg}</math>, <math>T_{eff}</math>, natural killer [NK] cells, B cells and eosinophils).

Tertiary/Exploratory	

To explore the association of genotype with PD, efficacy and safety of RO7049665.

	

Correlation analysis of single nucleotide polymorphisms with PD, efficacy and AEs.

### 4. STUDY DESIGN

#### 4.1 OVERALL DESIGN

Study WP40161 is a multicenter, randomized, adaptive, Investigator and participant blind, placebo-controlled study to investigate the safety, tolerability, PK, PD, and

preliminary efficacy of multiple ascending doses (MAD) of RO7049665 on top of standard of care (SOC) in participants with endoscopic evidence of moderate to severely active UC. The participants, investigators, and site personnel will be blinded to treatment assignments.

Since this is the first clinical study in which RO7049665 will be tested in participants diagnosed with UC and the first study in which multiple doses of RO7049665 will be administered, a dose escalation design will be used.

All participants in the study will have evidence of active disease on endoscopy at screening (MCS  $\geq 5$ , Endoscopy subscore of the Mayo Clinic Score [MCS-ES]  $\geq 2$ , stool frequency subscore  $\geq 1$ , and rectal bleeding subscore  $\geq 1$ ). Participants will be eligible for the study if they are currently receiving non-biologic SOC therapy for UC and have not been treated with any biologic therapy within 3 months (or 5 half-lives, whichever is longer) before the start of screening.

Participants will be randomized in a 4:1 ratio to receive multiple SC injections of RO7049665 or placebo, respectively (approximately 8 on active and 2 on placebo per cohort). Participants will receive their first doses in a staggered manner, with a five-day interval between the *first dose of the first, second, and third participants*. *The fourth participant can receive the first dose 14 days after the first dose of the third participant, at the earliest. There will be a 48-hour interval between the first dose of subsequent participants in each dose level.* Based on emerging data, dose levels may be expanded.

The dosing interval will be every 2 weeks (Q2W), for 4 doses. The first dose level will be 3.5 mg, the second dose level will be 7.5 mg *and participants enrolled in the cohorts of dose level 3 will receive 15 mg of RO7049665 (or placebo).* The doses are based on safety, tolerability, PK and PD data derived from study WP39826 (see Section 4.3) and *review of data from completed cohorts in this study.* Each dose level will have cohorts of approximately 10 participants, randomized in the ratio of 4:1 RO7049665 to placebo. Based on the emerging data there may be more than one cohort enrolled per dose level.

The second dose level may run in parallel with the first (see Section 1.2), after completion of recruitment into the lower dose level. However, prior to enrolling participants into the higher dose level, there will be an assessment of safety, tolerability, ADA, PK and selected PD data from at least 5 participants (4 on RO7049665, 1 on placebo) in dose level 1 who have received at least 8 weeks of treatment.

An overview of the study design is provided in Section 1.2.

